## 5.11 Safety Analyses

The safety analyses will be presented by the treatment received for the safety analysis set.

### 5.11.1 Adverse Events

Treatment emergent adverse events (TEAE) are reported according to protocol as any AE that has an onset on or after the dose of study drug or any pre-existing condition that has worsened on or after the first dose of study drug. The following TEAE flag will be applied to distinguish AEs from TEAEs:

- Any AE that has a start date and time on or after the first dose of study drug

A treatment-related AE is defined as an AE with a causality of “Possibly Related”, “Probably Related”, or “Related” to LY3885125. If an AE has missing relationship it is assumed to be related to the study drug for analysis purposes.

Maximum severity (Severe) will be assumed for an AE with missing severity.

Events that occur after the last follow-up visit or early termination visit will only be included in any TFLs if they are “Possibly Related”, “Probably Related”, or “Related” to LY3885125.

The following tables will be presented for AEs incidence and/or number of events will be reported as appropriate, by treatment group and overall:

- Overall summary of TEAEs
- TEAEs by system organ class and preferred term
- Treatment related TEAE by system organ class and preferred term
- Serious TEAE by system organ class and preferred term
- TEAE by system organ class, preferred term and maximum severity
- TEAE by system organ class, preferred term and relationship
- TEAEs leading to early withdrawal by system organ class and preferred term
- Listing of Serious TEAEs (presented in the Table section of the appendices).
- Listing of Deaths (presented in the Table section of the appendices).

Adverse event incidence is counted only once per system organ class and once per preferred term. The number and percent of participants experiencing events are reported. Outputs reported at maximum severity show the highest severity reported by a patient per system organ class and preferred term.

All AEs will be listed.

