### **9.3.2. Primary Endpoint(s) Analysis**

The primary endpoints in Part A and in Part B are AEs and SAEs. The analyses for AEs and SAEs will focus on events that emerge or worsen after the first dose of LY3885125. Events that occur after the last follow-up visit or early termination visit will only be included in an analysis if the investigation believes the event is at least possibly related to LY3885125.

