##### **Events Meeting the AE Definition**

- Any abnormal laboratory test results (hematology, clinical chemistry, or urinalysis) or other safety assessments (for example, electrocardiogram [ECG], radiological scans, vital signs measurements), including those that worsen from baseline, considered clinically significant in the medical and scientific judgment of the Investigator (that is, not related to progression of underlying disease).
- Exacerbation of a chronic or intermittent pre-existing condition including either an increase in frequency and/or intensity of the condition.
- New condition detected or diagnosed after administration of study intervention even though it may have been present before the start of the study.
- Signs, symptoms, or the clinical sequelae of a suspected drug-drug interaction.
- Medication error, misuse, or abuse of study intervention, including signs, symptoms, or clinical sequelae.

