PCSK9	proprotein convertase subtilisin/kexin type 9
PD	pharmacodynamic(s)
PK	pharmacokinetic(s)
CCI	
PT	prothrombin time
PUC	preparative ultracentrifugation
QTc	corrected QT interval
QTcF	QT interval corrected using Fridericia’s formula
RBC	red blood cell
RNA	ribonucleic acid
S1P	site-1 protease
S2P	site-2 protease
SAD	single ascending dose
SAE	serious adverse event
SAP	statistical analysis plan
SRC	Safety Review Committee
SC	subcutaneous(ly)
SCAP	SREBP cleavage activating protein
screen	The act of determining if an individual meets minimum requirements to become part of a pool of potential candidates for participation in a clinical study.
siRNA	small interfering RNA
SoA	Schedule of Activities
SREBP	sterol regulatory element-binding protein
SREBP1a	sterol regulatory element-binding protein 1 isoform a
SREBP1c	sterol regulatory element-binding protein 1 isoform c
SREBP2	sterol regulatory element-binding protein 2
t1/2	half-life
T2DM	Type 2 diabetes mellitus (T2DM)

Term	Definition
TBL	total bilirubin
TEAE	Treatment-emergent adverse event: An untoward medical occurrence that emerges during a defined treatment period, having been absent pretreatment, or worsens relative to the pretreatment state, and does not necessarily have to have a causal relationship with this treatment.
TG	triglyceride
Tmax	time of maximum observed concentration
TSH	thyroid-stimulating hormone
ULN	upper limit of normal
UK	United Kingdom
US	United States
USP	United States Pharmacopeia
VLDL	very low-density lipoprotein
WBC	white blood cell

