## 10 LIST OF TABLES, FIGURES AND LISTINGS

The following table includes details of the tables, figures and listings to be included within each section of the eCTD. The eCTD section is shown in bold. The following validation methods maybe used:

- Independent programming of numbers and manual review of format (IP)
- Independent programming by statistician of numbers and manual review of format (Stat IP)
- Manual review (MR)
- Code review (CR)

Section Number	Table Number	Table Title	Validation Method	Shell Number (if repeat)
14.1.1	Participant Disposition			
	14.1.1.1	Participant Disposition, Part A – Screened Set	IP	-
	14.1.1.2	Screening Failures – All Participants	IP	-
14.1.2	Protocol Deviations			
	14.1.2.1	Protocol Deviations, Part A – Safety Analysis Set	IP	-
14.1.3	Demography, Baseline Characteristics, Treatment Compliance, and Analysis Sets			
	14.1.3.1	Analysis Sets, Part A – Screened Set	IP	-
	14.1.3.2	Demographics, Part A – Full Analysis Set	IP	-
	14.1.3.3.1	Previous Medical History by System Organ Class and Preferred Term, Part A – Full Analysis Set	IP	-
	14.1.3.3.2	Ongoing Medical History by System Organ Class and Preferred Term, Part A – Full Analysis Set	IP	14.1.3.3.1
14.3	Safety Data			
14.3.1	Adverse Events			
	14.3.1.1	Overall Summary of Treatment Emergent Adverse Events, Part A – Full Analysis Set	IP	-
	14.3.1.2	Treatment Emergent Adverse Events by System Organ Class and Preferred Term, Part A – Safety Analysis Set	IP	-
	14.3.1.3	Treatment-Related Treatment Emergent Adverse Events by System Organ Class and Preferred Term, Part A – Safety Analysis Set	IP	14.3.1.2

QMD Ref: Worldwide-TMP-ST-054-1.0_Effective: 12Aug2022	Governing QMD: Worldwide-SOP-ST-026
Confidentiality Statement This document is the property of Worldwide Clinical Trials Inc. and may not be duplicated, copied, altered or removed from company without prior approval from Worldwide Quality Assurance or in compliance with Worldwide Standard Operating Procedures.	

Worldwide Clinical Trials Controlled Quality Management Document		
 WORLDWIDE CLINICAL TRIALS	Sponsor:	Eli Lilly and Company
	Protocol Number:	J4N-MC-YFAA
STATISTICAL ANALYSIS PLAN		

Section Number	Table Number	Table Title	Validation Method	Shell Number (if repeat)
	14.3.1.4	Serious Treatment Emergent Adverse Events by System Organ Class and Preferred Term, Part A – Safety Analysis Set	IP	14.3.1.2

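### The TEAE flag tests only the AE start date and omits post-dose worsening, so TEAEs may be undercounted; the overall TEAE table also names the wrong analysis set

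*SAP*

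**What the plan says.** **TEAE definition and flag.** SAP Section 5.11.1 gives a definition with two limbs. One is onset on or after the dose. The other is "any pre-existing condition that has worsened on or after the first dose of study drug". The single-line flag that follows, which is meant to separate TEAEs from other AEs in the data, is "Any AE that has a start date and time on or after the first dose of study drug".

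**Protocol.** Section 9.3.2 directs the primary analysis at "events that emerge or worsen after the first dose of LY3885125". The TEAE entry in Appendix 7 (Section 10.7) likewise covers an occurrence that was absent before treatment "or worsens relative to the pretreatment state". SAP Section 8 declares no changes from the protocol's analysis.

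**Analysis set.** SAP Section 5.11 says that safety analyses are "presented by the treatment received for the safety analysis set". SAP Sections 2 and 5.1.3 and Protocol Section 9.2 make the same assignment. In SAP Section 10, however, Table 14.3.1.1 is titled "Overall Summary of Treatment Emergent Adverse Events, Part A – Full Analysis Set". The remaining TEAE summaries, 14.3.1.2 to 14.3.1.7 (one of them numbered 13.3.1.6), name the Safety Analysis Set.

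**The concern.** AEs and SAEs are the only primary endpoints, and every TEAE table depends on the flag. A programmer will code the flag line rather than the sentence above it. If the flag is narrower than the definition, the tables do not deliver the analysis that the protocol describes, and the SAP does not record the difference. The omission can only remove TEAEs, never add them.

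The analysis-set label is a separate matter. The Full Analysis Set is everyone randomised (SAP Section 5.1.2), and the Safety Analysis Set is everyone exposed (Section 5.1.3). If the two differ, the overview table and the detailed tables would show different column totals and percentages for the same events.

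**Working it through.** **1. Which events fall in the gap.** AEs are collected from signature of consent (Protocol Section 8.3.1), and screening can run up to 28 days before dosing (Section 4.1.1.1). An AE can therefore start before the first dose. The cases are:

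| Event | Meets the SAP definition? | Passes the flag? |
|---|---|---|
| AE starting after the dose | Yes | Yes |
| Medical-history condition that worsens after the dose, entered as an AE dated from the worsening | Yes | Yes |
| AE with missing start, unclear whether before or after dose (SAP Section 5.2.5.1) | Treated as yes | Yes, by default |
| AE starting before the dose and unchanged afterwards | No | No |
| AE starting before the dose, worsening afterwards, new record opened | Yes | Yes |
| AE starting before the dose, worsening afterwards, same record kept | Yes | **No** |

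Only the last row is lost. The recording and follow-up rules in Protocol Section 10.3.4 do not say whether such a worsening opens a new record.

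**2. Denominators.** Reading the allocation ratios in Protocol Section 4.1.1 as numbers per cohort gives 2 × (6 + 2) + 3 × (9 + 2) + (10 + 9) = 16 + 33 + 19 = 68, which matches the Part A total in Protocol Section 9.5. Cohort 6 was not run (SAP Section 3), so the planned total is 16 + 33 = 49. Of these, 6 + 6 + 9 + 9 + 9 = 39 receive LY3885125 and 5 × 2 = 10 receive placebo. The number printed for Cohorts 1 and 2 in the SAP Section 4 table does not fit these ratios and looks like a redaction artefact; it was not used.

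**3. Size of the flag effect.** One participant whose only TEAE, overall or in a given table row, is an unflagged worsening changes the percentage by 100/N:

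- dose arm of 6: 100/6 = 16.7 points
- dose arm of 9: 100/9 = 11.1 points
- pooled placebo: 100/10 = 10.0 points
- pooled LY3885125: 100/39 = 2.6 points

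**4. How likely it is to occur.** The documents give no rate. Suppose each of the 49 participants independently has such a record with probability p (an assumption). The chance of at least one is 1 − (1 − p)^49:

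- p = 1%: 39%
- p = 2%: 63%
- p = 5%: 92%
- p = 10%: 99%

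If the eCRF always opens a new record at worsening, p = 0 and so is the effect.

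**5. Size of the analysis-set effect.** Randomisation is on Day -1 (Protocol Section 6.3) and dosing on Day 1 (Section 4.1.1.2), so a participant can be randomised and not dosed; Protocol Section 7.3 allows for such participants. Assume one undosed participant in the column, and a TEAE in about half of the column:

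| Column | Full Analysis Set | Safety Analysis Set | Difference |
|---|---|---|---|
| Arm of 6 | 3/6 = 50.0% | 3/5 = 60.0% | 10.0 points |
| Arm of 9 | 4/9 = 44.4% | 4/8 = 50.0% | 5.6 points |
| Pooled LY3885125 | 19/39 = 48.7% | 19/38 = 50.0% | 1.3 points |
| Pooled placebo | 5/10 = 50.0% | 5/9 = 55.6% | 5.6 points |

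If the undosed participant is replaced, as Protocol Section 9.5 permits, an arm of 6 dosed becomes 7 randomised. A single case is then 1/7 = 14.3% in the overview and 1/6 = 16.7% elsewhere. If everyone randomised was dosed, every difference is zero.

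**The case against.** The strongest reply is that much of the worsening limb is already covered. Protocol Section 10.3.1 counts as an AE "Exacerbation of a chronic or intermittent pre-existing condition including either an increase in frequency and/or intensity of the condition". A post-dose exacerbation reported that way has a post-dose start date and passes the flag. That stands, and it confines the gap to AEs that began between consent and dosing and kept one record. How those were recorded depends on eCRF instructions that are not in these documents.

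The data are not hidden either. All AEs are listed, unclear start dates default to treatment-emergent, and the safety comparison is descriptive only. This is correct: the issue is classification in the summary tables, not data capture.

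On the analysis set, the label on Table 14.3.1.1 is probably a title slip. The same list mislabels other items: medical history and medications are shown on the Full Analysis Set although SAP Sections 5.7 and 5.8 say Safety. That explains the label but does not correct it.

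Three stronger readings go too far:

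- A reader might infer that the primary endpoint is in fact miscounted. The documents do not show that any affected record exists.
- A reader might infer that the analysis-set label changes event counts. An undosed participant has no first dose and cannot meet the flag, so normally only N and percentages move. The narrow exceptions are an AE defaulted to treatment-emergent because its date is missing, and columns built by randomised rather than received treatment.
- A reader might infer from the drug name in Protocol Section 9.3.2 that placebo events are left out. The SAP flag already refers to study drug, so no change is needed there.

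**Conclusion.** The concern holds in a limited form. The flag in SAP Section 5.11.1 is wrong as written: it contradicts the definition directly above it and the protocol's primary analysis, with no declared change. The consequence is a possible undercount of 2.6 to 16.7 points per affected participant, depending on the column. This assumes that worsening can be kept under a pre-dose start date and that the participant has no other TEAE counted in that row. The number affected cannot be known from the documents and may be zero.

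The Full Analysis Set label on Table 14.3.1.1 breaks the SAP's own rule. It matters only if a randomised participant was not dosed, and then it normally lowers the percentages in that one table without changing the counts. All denominators here are planned numbers, not achieved ones.

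**What to change.** 1. Make the flag match the definition in one of two ways.
   - Extend it with: *or an AE or pre-existing condition with onset before the first dose that worsens on or after the first dose of study drug*.
   - Or state in SAP Section 5.11.1 that any post-dose worsening is entered as a new AE record with its own start date.

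   The choice depends on the eCRF. The first option needs something in the data that dates the worsening, and neither document shows a severity-change record. The second is sound only if the data were collected that way. Since the study stops after Cohort 5, this should be checked against the completed AE records that start before dosing.
2. Relabel Table 14.3.1.1 to the Safety Analysis Set.

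The cost is one clause or sentence, one table title, a small programming change and a review of the pre-dose AE records. SAP Section 5 requires the SAP and shells to be approved before Part A database lock. After lock, the same change needs a post-lock addendum.

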### **7.1. Discontinuation of Study Intervention**

It may be necessary for a participant to permanently discontinue study intervention (applies only to Part B). If study intervention is permanently discontinued, the participant will remain in the study to complete procedures for an early termination visit and post-treatment follow-up, if applicable, as shown in the SoA (Section 1.3).

In Part B, prior to the repeat dose, all available safety data will be reviewed. Any clinically significant findings that may determine if further dosing should be discontinued will be determined by the Investigator in consultation with the Sponsor. A second dose will not be administered if the study participant experienced a hypersensitivity reaction after receiving the first dose in Part B of the study.

A participant should be permanently discontinued from study intervention if:

- The participant becomes pregnant during the study
- The participant decides to discontinue study intervention
- The Investigator decides that the participant should be discontinued due to AEs (the participant will be followed until the AE resolves)
- The participant has a SAE considered related to study treatment.

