## **7.2. Participant Discontinuation/Withdrawal from the Study**

A participant may withdraw from the study:

- At any time at the participant's own request for any reason or without providing any reason.
- At the request of the participant's designee (for example, parents or legal guardian).
- At the discretion of the investigator for safety, behavioral, compliance, or administrative reasons.
- If enrolled in any other clinical study involving an investigational product, or enrolled in any other type of medical research judged not to be scientifically or medically compatible with this study.
- If the participant, for any reason, requires treatment with a therapeutic agent that is prohibited by the protocol and has been demonstrated to be effective for treatment of the study indication. In this case, discontinuation from the study occurs prior to the introduction of the new agent.

At the time of discontinuation from the study, if possible, the participant will complete procedures for an early discontinuation visit and post-treatment follow-up, if applicable, as shown in the SoA (Section 1.3). If the participant has not already discontinued study intervention, the participant will be permanently discontinued from the study intervention at the time of the decision to discontinue the participant from the study.

If the participant withdraws consent for disclosure of future information, the Sponsor may retain and continue to use any data collected before such a withdrawal of consent. If a participant withdraws from the study, the participant may request destruction of any samples taken and not tested, and the Investigator must document this in the site study records.

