**8.3.1. Timing and Mechanism for Collecting Events**

This table describes the timing, deadlines, and mechanism for collecting events:

Event	Collection Start	Collection Stop	Timing for Reporting to Sponsor or Designee	Mechanism for Reporting	Back-up Method of Reporting
Adverse Event					
AE	Signing of the ICF	Participation in study has ended	As soon as possible upon site awareness	AE CRF	N/A
Serious Adverse Event					
SAE and SAE updates – prior to start of study intervention and deemed reasonably possibly related to study procedures	Signing of the ICF	Start of intervention	Within 24 hours of awareness	SAE paper form	SAE paper form
SAE and SAE updates – after start of study intervention	Start of intervention	Participation in study has ended	Within 24 hours of awareness	SAE paper form	SAE paper form
SAE* – after participant's study participation has ended and the Investigator becomes aware	After participant's study participation has ended	N/A	Promptly	SAE paper form	N/A

Event	Collection Start	Collection Stop	Timing for Reporting to Sponsor or Designee	Mechanism for Reporting	Back-up Method of Reporting
Pregnancy					
Pregnancy in female participants and female partners of male participants	After the start of study intervention	The predicted time until estimated plasma levels of partner would be below the level of toxicologic concern, plus 93 days	Within 24 hours (see Section 8.3.2)	Pregnancy paper form	Pregnancy paper form
Product Complaints					
PC associated with an SAE or might have led to an SAE	Start of study intervention	End of study intervention	Within 24 hours of awareness	Product Complaint form	N/A
PC not associated with an SAE	Start of study intervention	End of study intervention	Within 1 business day of awareness	Product Complaint form	N/A
Updated PC information	—	—	As soon as possible upon site awareness	Originally completed Product Complaint form with all changes signed and dated by the Investigator	N/A
PC (if Investigator becomes aware)	Participation in study has ended	N/A	Promptly	Product Complaint form	

Abbreviations: AE = adverse event; CRF = case report form; ICF = informed consent form; N/A = not applicable; PC = product complaint; SAE = serious adverse event

\*Serious adverse events should not be reported unless the Investigator deems them to be possibly related to study treatment or study participation.

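### SAP 5.11.1 applies its causality filter on late events to listings as well as tables, so a recorded unrelated SAE or death could be left off the SAE and death listings

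*SAP*

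**What the plan says.** SAP 5.11.1 sets the rule: "Events that occur after the last follow-up visit or early termination visit will only be included in any TFLs if they are" given one of the three causality ratings, from possible upwards, that the SAP counts as drug-related. No exception is written for serious events or deaths. The outputs named in that section include a listing of serious TEAEs and a listing of deaths. The section ends its account of outputs with "All AEs will be listed". It also protects events with no causality rating: "If an AE has missing relationship it is assumed to be related to the study drug for analysis purposes".

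The rule comes from protocol 9.3.2: "Events that occur after the last follow-up visit or early termination visit will only be included in an analysis if" they are believed to be at least possibly related to the drug. SAP section 8 states that nothing in the planned protocol analysis has changed.

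On collection, protocol 8.3.1 sets the stop for AEs and for post-dose SAEs at "Participation in study has ended". Its note on SAEs after that point asks for a report only if the investigator considers the event possibly related to study treatment or to study participation. On withdrawal, protocol 7.2 says that, if possible, "the participant will complete procedures for an early discontinuation visit and post-treatment follow-up, if applicable, as shown in the SoA". Protocol 7.3 provides for a vital-status search covering all randomized participants and for documenting any death found.

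**The concern.** The primary endpoint of Part A is AEs and SAEs, with no causality condition. A causality filter on summary tables is a choice of analysis window, and the protocol makes that choice openly. A causality filter on listings is different in kind, because listings are where a reader of the study report expects to see every recorded event and to judge causality independently. If the filter reaches them, an investigator's rating decides whether a recorded death is visible at all.

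This is a first-in-human trial of a drug whose effect, by protocol 4.3.4, may last for months after one dose. Protocol 4.5.3 has the Safety Review Committee weigh severe and life-threatening events whatever their attribution. Outputs that can omit a recorded death because it was rated unrelated do not fit that stance. The SAP also gives its programmers two instructions that cannot both be followed for such an event.

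**Working it through.** **1. The three statements side by side**

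- Protocol 9.3.2: late events enter an analysis only if at least possibly related.
- SAP 5.11.1, filter: late events enter any table, figure or listing only if at least possibly related to LY3885125.
- SAP 5.11.1, listing rule: all AEs are listed.

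The filter and the listing rule conflict for any late event rated unrelated. The filter is also wider than the protocol rule, and SAP section 8 does not report this.

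The titles in SAP section 10 for the AE listing (16.2.7.1), the deaths listing (14.3.2.1) and the SAE listing (14.3.2.2) carry no causality restriction, so they do not settle the conflict. The deaths listing takes its shell from the AE listing, so it would presumably inherit whatever filter is applied there.

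**2. Which late events can reach the database**

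| Late event | How it could be recorded | Listings under the filter | Listings under the listing rule |
|---|---|---|---|
| Rated related to the drug | Protocol 8.3.1 | Kept | Kept |
| Causality missing | Any route | Kept (counted as related) | Kept |
| Unrelated event during contact after ET | Protocol 7.2, where applicable; AE follow-up under 8.3 | Omitted | Kept |
| SAE attributed to study participation, not to the drug | Note to protocol 8.3.1 | Omitted | Kept |
| Unrelated death found by the vital-status search | Protocol 7.3 | Omitted | Kept if entered as an AE |

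The fourth row matters most. Protocol 8.3.1 asks for such an SAE after participation has ended, yet the SAP filter tests only relatedness to LY3885125. An event the protocol asks sites to report would then be left out.

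**3. Denominators, for scale only**

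The cohort sizes follow from the allocation ratios in protocol 4.1.1 and the Cohort 6 size in protocol 9.5:

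2 × (6+2) + 3 × (9+2) + 19 = 16 + 33 + 19 = 68.

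This reproduces the approximately 68 in protocol 9.5. Cohort 6 was not enrolled, which leaves 68 − 19 = 49:

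- active: 2×6 + 3×9 = 39
- placebo: 5×2 = 10

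One participant moves an incidence row by 1/n:

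- 1/6 = 16.7 points and 1/9 = 11.1 points in a dose group
- 1/39 = 2.6 points in pooled LY3885125
- 1/10 = 10.0 points in pooled placebo

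These figures show how much one person counts. They are not an expected bias. In a listing, the effect is one entry or none.

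**4. How likely, under stated assumptions**

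The documents give neither an early-termination rate nor a late-event rate. Let m be the number of early terminators among 49, and q the chance that each has a recorded unrelated SAE or death after ET. The chance of at least one is 1 − (1−q)^m.

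| Early termination (assumed) | m | q = 1% | q = 5% |
|---|---|---|---|
| 5% | 2 | 2.0% | 9.8% |
| 10% | 5 | 4.9% | 22.6% |
| 20% | 10 | 9.6% | 40.1% |

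Because q counts only recorded events, the reporting limits in protocol 8.3.1 point to the low end.

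**The case against.** The strongest reply is that the rule hardly ever operates in the population this SAP covers, and most of that reply stands.

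- The SAP analyses single-dose Part A only. Protocol 7.1, on stopping treatment while staying in the study, is expressly confined to Part B. Its provision for following a participant until an AE resolves also concerns an event that has already begun, not one with onset after ET.
- ET is the last column of the Part A schedule of activities, and completers receive the ET assessments at their final visit, apart from the PCSK9 sample. ET therefore works as the end of observation. Follow-up after it under protocol 7.2 is only where applicable.
- After participation ends, protocol 8.3.1 asks for SAEs only if possibly related to treatment or participation. Most unrelated late events would never be recorded.
- Missing causality counts as related, and the rule covers completers after their last visit as well as early terminators.

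A reader might infer something stronger: that unrelated SAEs and deaths in withdrawn participants vanish from the primary endpoint and distort the incidence tables. The documents do not support that. Protocol 9.3.2 itself defines the primary endpoint analysis with this cut-off, so the tables follow a prespecified window. No statistical comparison of safety endpoints is planned (protocol 9.3.5). It also cannot be said that the events are dropped from every listing, because the same SAP section promises that all AEs are listed.

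The reply does not dispose of the listings. The routes in protocol 7.2, 7.3, 8.3 and 8.3.1 are narrow but real, and for an event that arrives by one of them the SAP gives contradictory instructions.

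**Conclusion.** The concern holds for the listings. SAP 5.11.1 contradicts itself on whether late events judged unrelated are listed, goes further than protocol 9.3.2, and is not declared as a change in SAP section 8. Read literally, it would keep a recorded unrelated late SAE or death out of the SAE and death listings.

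The size is one listing entry or none for each such event, and few are expected. That expectation rests on the Part A design (ET normally the final visit, collection ending with participation), not on any rate in the documents. No figure in the plan is shown to be wrong, and no bias in the incidence tables is demonstrated. It is still worth correcting before lock, because an unlisted death cannot be seen by anyone reading the report.

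**What to change.** In SAP 5.11.1, replace 'any TFLs' with 'summary tables', which matches protocol 9.3.2. Add one sentence: every recorded AE, SAE and death is listed whatever its causality, with a flag for onset after the last follow-up or ET visit. State which of the two visits sets the flag for a participant who has both, so that it can be programmed without interpretation.

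Protocol 9.3.2 needs no change, and the statement in SAP section 8 then becomes accurate on this point. The summary tables are unaffected.

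The cost is one sentence, one programming condition and possibly a few more unrelated events in the listings. SAP section 5 requires approval of amendments before the Part A database lock. After lock, the same text would go into the post-lock addendum described there.
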